10.4. Clinical data set

Inclusion. Check for inclusion and exclusion criteria and randomisation. Informed Consent Form.**Baseline registration and investigations.**

Signs and symptoms at ER and management plan

Participant background

Vaccination

Co-morbidities and chronic medication

Standard of care haematology and biochemistry

EQ-5D-5L questionnaire

Management: Clinical decision after randomisation and initial results

Investigations: respiratory, urine, faeces, blood, SARS-CoV-2, radiology (only when standard of care)

Day 14: symptoms, EQ-5D-5L questionnaire

Day 30: symptoms, EQ-5D-5L questionnaire

Month 3 (if applicable): symptoms, EQ-5D-5L questionnaire

Month 6 (if applicable): symptoms, EQ-5D-5L questionnaire

Outcomes and safety:

Antibiotic treatment

Antiviral and antifungal agents

Hospital course

Device deficiency

(Severe) Adverse Event

Deviation

End of study

Table 1. Visit Schedule

Procedures	Screening	Enrollment	Hospitalization Period ^e	Face to face, on line questionnaire or phone call		Phone call Extended FU	Phone call Extended FU
	Pre- study procedures	Day 1	> Day 1	Day 14	Day 30	3 months ^f	6 months ^f
	Day 1						
Informed consent	X						
Eligibility criteria	X						
Demographics ^a	X						
Baseline assessment ^b	X						
Vaccination status	X						
Comorbidities and chronic medications	X						
Hospital course ^c		X	X ^e				
Microbiological testing ^d		X	X				
Concomitant therapy review	X	X	X ^e	X	X	X ^f	X ^f
Symptoms review and hospitalizations	X	X	X ^e	X	X	X ^f	X ^f
Quality of life questionnaire EQ5D		X		X	X	X ^f	X ^f

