13. STATISTICAL CONSIDERATIONS

13.1. Sample size calculation

Co-primary endpoints used in the study:

1. Days on antibiotic treatment within 14 days (superiority endpoint)
2. Days alive out of the hospital within 14 days (superiority endpoint)
3. Adverse outcome within 30 days (non-inferiority safety endpoint)

Required sample sizes are presented for endpoint 2 and 3. Endpoint 1 is non-limiting due to having an expected smaller standard deviation compared to endpoint 2 and having the same clinically relevant effect size.

The intervention is considered successful if superiority is demonstrated for either or both endpoints 1 and 2 AND non-inferiority is demonstrated for endpoint 3. We use a hierarchical nested design: superiority primary endpoints are tested first. Only if superiority to at least one of the two superiority endpoints is confirmed, the non-inferiority safety endpoint is taken into consideration. To maintain an overall alpha < 0.05, the two superiority endpoints will be tested using a two-sided alpha of 0.025, while the non-inferiority endpoint will be tested using a one-sided alpha of 0.05. The minimal power for the superiority endpoints is set to 0.9 and for the non-inferiority endpoint to 0.95. This is to maintain overall power of the trial, given the hierarchical testing. For 'Adverse outcome' we considered different non-inferiority margins. For 'Days on antibiotic treatment' and 'Days alive out of the hospital' we defined 1 day as a clinically relevant effect size.

The distribution of endpoint 2 is yet unknown for the ARI population. We supported our sample size calculation using data of patients presenting with CAP to Dutch ERs and hospitalised to a non-ICU ward (ClinicalTrials.gov: NCT02604628). The standard deviation (SD) of 'Days alive out of the hospital within 14 days' in this population was 4 days. The theoretical maximum SD with a 14 days follow-up period is 7 (which would be the case if 50% had zero days and 50% had 14 days alive out of the hospital). However, we expect that in the target population the variability for this endpoint will be less than in the CAP population. We varied the SD to assess the impact on

the sample size. We used a standard correction factor of 1.15 for non-normality of the data. (Table 1) Hence for the superiority endpoints a sample size of 457 per arm would be adequate.

Table 1: Sample sizes for Days alive out of the hospital using different assumptions

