13.2. Analysis populations

A statistical analysis plan will be prepared after protocol approval and once site selection process has been initiated.

The main analyses will be performed for the total population

Analyses will be stratified by:

- age groups (i.e. 18-49, 50-65, >65)
- clinical syndrome: exacerbation of chronic pulmonary disease, influenza-like illness, laryngitis/laryngotracheitis (croup), acute bronchitis
- risk factors. Patient groups at risk for developing severe disease are well known, such as the elderly, patients with chronic pulmonary, cardiovascular or metabolic disease or immunocompromised patients. Clinical predictors of severity are also well known. Still,

within risk groups may exist the uncertainty whether to hospitalise and/or to treat and the impact of testing may be assessed.

- Vaccination status. Influenza. Pneumococcal.

The primary analysis will follow the intention-to-treat principle in which groups are compared based on the allocated regimen. In the per protocol analysis we will exclude participants not receiving the test according to the randomised regimen (e.g. randomised to rapid syndromic testing but not receiving the test).

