13.3. Primary study parameter(s)

Descriptive statistics will be produced and tabular summaries will be presented, stratified according to the allocated group (rapid syndromic testing vs. control). Categorical data will be summarized by the number and percentage of patients in each category. Appropriate summary statistics will be used for continuous variables depending on the distributional assumptions. These include measures of central tendency (mean or median) and dispersion (standard deviation or inter-quartile range).

‘Days on antibiotic treatment’ and ‘Days alive out of the hospital’ will be analysed using a linear regression analysis, including as covariates stratification by age groups and predefined risk factors. Upfront we may expect that the assumption of normally distributed residuals is violated, in which case we will determine the confidence interval by bootstrapping.

Adverse outcome will be analysed using Cox proportional hazards regression adjusted for age groups and predefined risk factors. Risk differences and 90% CI will be inferred by comparing the cumulative incidence of failure at day 30 from the Cox model and bootstrapping for the confidence interval. A 90% CI will be used to be compatible with a one-sided alpha of 0.05.

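### The co-primary models adjust for age only in groups; a prespecified spline on continuous age would recover a little precision, mainly in the two linear models

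*Combined protocol and SAP*

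**What the plan says.** Section 13.3 describes the linear regression for antibiotic days and days alive out of hospital as "including as covariates stratification by age groups and predefined risk factors". For the third co-primary endpoint it says: "Adverse outcome will be analysed using Cox proportional hazards regression adjusted for age groups and predefined risk factors". The non-inferiority result is a risk difference with a 90% CI, obtained by "comparing the cumulative incidence of failure at day 30 from the Cox model" and bootstrapping.

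Section 13.3 does not define the age groups. The only definition is in section 13.2, in the list of factors for stratified analyses: "age groups (i.e. 18-49, 50-65, >65". The same list names the elderly among the patients at risk of severe disease. Randomisation is stratified by centre only (section 10.2), and there is no upper age limit (sections 8.1 and 8.2).

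On the recording of age, the visit schedule in section 10.4 has a row "Demographics ^a", whose footnote is not in the available text. On the SAP, section 13.2 says: "A statistical analysis plan will be prepared after protocol approval and once site selection process has been initiated". That SAP is not among the documents.

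**The concern.** Three groups are a sensible way to display subgroups but a coarse way to adjust. The top group has no upper bound, so the model treats patients of 66 and 90 as the same age. The protocol itself regards older patients as a risk group (sections 4.1 and 13.2). If the outcome changes with age inside a group, that variation stays in the residual and the interval for the treatment effect is slightly wider than it need be. Chance imbalance in age within a group is also left uncorrected, because age is not a stratification factor.

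A second, smaller point is that age could enter the model twice, once as the groups and again as the elderly among the risk factors.

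What is at stake is a little precision on the co-primary estimates, chiefly the two from linear models.

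**Working it through.** **Inputs from section 13.1.** The effect size is 1 day and the SD is 4 days (3 to 7 tabulated). The non-normality factor is 1.15. Power is 0.90 for superiority and 0.95 for non-inferiority. On error rates, "the two superiority endpoints will be tested using a two-sided alpha of 0.025" and "the non-inferiority endpoint will be tested using a one-sided alpha of 0.05". Adverse-outcome incidence is 5% or 10%, the margin is 5 percentage points, and the total is 1600.

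**Inputs that must be assumed.** These are the age distribution, the shape of the age effect, and R² (the share of outcome variance that age explains). None is in the documents.

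**Step 1: the plan's own figures.**
- Superiority: n = 1.15 × 2 × SD² × (2.2414 + 1.2816)² / 1². With SD 4 this is 456.7, so 457 per arm, as stated. SD 3, 5, 6 and 7 give 257, 714, 1028 and 1399, all as tabulated.
- Non-inferiority: n = 2 × p(1 − p) × (1.6449 + 1.6449)² / 0.05² gives 780 at 10% and 412 at 5%, as stated.

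Neither formula contains a covariate term, so the sample size takes no credit for adjustment and does not depend on how age is coded.

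**Step 2: loss from grouping in a linear model.** Let c be the share of the age signal that the groups keep. Relative residual variance is 1 − cR² with groups and 1 − R² with age correctly modelled on its continuous scale. The loss of effective sample size is 1 − (1 − R²)/(1 − cR²).

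**Step 3: c.** Four assumed age distributions were tried: uniform 18-90, and normal with mean (SD) 60 (18), 68 (16) and 50 (18). For a linear age effect, c is 0.861, 0.817, 0.760 and 0.807. For an exponential rise, c is 0.770, 0.585, 0.483 and 0.679.

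**Step 4: results.**

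| R² | Loss at c = 0.80 | Patients of 1600 | Loss at c = 0.60 |
|---|---|---|---|
| 0.02 | 1 − 0.98/0.984 = 0.41% | 7 | 1 − 0.98/0.988 = 0.81% |
| 0.05 | 1 − 0.95/0.96 = 1.04% | 17 | 1 − 0.95/0.97 = 2.06% |
| 0.10 | 1 − 0.90/0.92 = 2.17% | 35 | 1 − 0.90/0.94 = 4.26% |

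At c = 0.80 the standard error changes by about 0.2%, 0.5% and 1.1%. The lowest simulated c, 0.483, gives 1 − 0.90/0.9517 = 5.4% at R² = 0.10. That needs both a steep rise at old age and an elderly population.

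**Step 5: what this means for the superiority tests.** Take R² = 0.05 and c = 0.80. The required n per arm at SD 4 is 457 × 0.96 ≈ 439 with groups and 457 × 0.95 ≈ 434 with continuous age. Power at 800 per arm is as follows.

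| SD | Unadjusted | Groups | Continuous age |
|---|---|---|---|
| 4 | 0.9923 | 0.9941 | 0.9945 |
| 5 | 0.932 | 0.941 | 0.944 |

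**Step 6: adverse outcome.** The linear formula does not carry over. A simulation of the standardised risk difference (n = 1600, 10% events, 1500 replicates, a logistic model standing in for the Cox model) gave variances 0.2%, 0.5% and 2.7% lower with continuous age, for assumed log-odds slopes of 0.2, 0.4 and 0.6 per 10 years. These ratios carry simulation error. By normal approximation at 800 per arm, power is Φ(0.05/0.015 − 1.645) = 0.954. A 0.5% cut in variance moves it to 0.955, and a 2.7% cut to 0.959.

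**Step 7: does the form matter?** If the age effect is a smooth threshold near 60, the groups keep 0.947, 0.909, 0.889 and 0.908 of the signal, against 0.913, 0.909, 0.893 and 0.881 for a straight line. Groups do as well or better in three of the four distributions, so a linear term alone is not a safe replacement.

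**The case against.** Adjusting for age groups is a valid analysis. Under randomisation it causes no bias and no inflation of type I error, and it improves on the unadjusted calculation behind the sample size. This stands in full: the loss is measured against a better analysis, not against anything the protocol promises.

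The formula in step 2 also treats age as the only covariate. Section 13.3 adjusts for risk factors as well, and chronic pulmonary, cardiovascular and metabolic disease would be expected to track age and take up part of the within-group signal. This stands, and it means the figures above are probably too high.

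Final covariate coding may be settled in the SAP still to be written. This mitigates the point but does not remove it, because the protocol wording commits the models to groups.

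A reader might infer more than the documents support:
- **That the loss is as large as 5%, or 80 of the 1600 patients.** This needs age alone to explain 20% of outcome variance (0.84/0.80 = 1.05 at c = 0.80). Nothing in the documents supports so strong an association.
- **That all three co-primary endpoints lose alike.** Step 6 shows that the day-30 risk difference gains little at modest age slopes.
- **That exact age is stated to be collected.** It is a strong inference, since checking the age criterion and assigning the groups both need it, but the text does not say so. It is likewise an inference that the section 13.2 cut-points are the covariate coding in section 13.3.
- **That the change is free.** It holds a gain only with a flexible form, and it may add parameters to bootstrapped models.

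**Conclusion.** The point holds as a minor efficiency suggestion. Grouped age discards some information, mainly in the two linear models. For R² of 0.02 to 0.10 and c = 0.80, the loss is about 0.4% to 2.2% of effective sample size, and probably less with the risk factors also in the model. A steep rise at old age would raise it (0.8% to 4.3% at c = 0.60), and a threshold-like effect would lower it. For adverse outcome it is slight unless age is strongly prognostic.

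All of these figures rest on assumed age distributions and age effects. The stated sample sizes reproduce exactly, and planned power, type I error and freedom from bias are untouched. The change is worth making because it costs almost nothing while the SAP is still to be written. In an open-label trial the functional form should be fixed before outcome data are seen.

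**What to change.** In section 13.3, or in the SAP:
- Enter age in the primary models as a continuous covariate through a restricted cubic spline, with few knots at positions fixed in advance and held fixed across bootstrap resamples.
- State that the elderly are not entered again as a separate risk factor.
- Keep 18-49, 50-65 and >65 for subgroup display only.
- Confirm that age, and not only age group, is recorded in the eCRF.

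The cost is a few lines of text. Three groups use two parameters and a restricted cubic spline with k knots uses k − 1, so three knots add none and four or five add one or two. The adverse-outcome model is where this matters most: at 5% to 10% incidence, 1600 patients yield only about 80 to 160 events, and the risk factors are in the model too. That argues for the fewest knots there.

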10.2. Randomisation and blinding

Due to the nature of the intervention, blinding is not possible. After all eligibility criteria have been verified and informed consent has been obtained, randomisation will be performed using the built-in randomisation module of the eCRF system. Allocation will be concealed until the moment of randomisation. To this end, block randomisation will be used with variable blocks of size 2, 4 and 6. Randomisation will be stratified by centre. After the decision to randomise the patient is made, patients will not be excluded from the trial. If the allocated intervention is not applied for any reason, this will be recorded and follow-up for the participant will be completed.

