10.3. Data collection

A secured electronic case record form (eCRF) will be specifically designed for this study for data capture.

- **Main study** (Follow up until 30 days) – Standard of care clinical and microbiological data will be collected but not study specific biological samples will be obtained for research purposes. The **clinical data set** will summarize the illness episode and outcome, microbiological testing and antimicrobial use including the total hospitalisation or, in case of discharge, the time window defined on the primary endpoints. Information including data for health economic analysis will be collected on day of enrolment, day 14 (visit window: day 14 – 16) and on day 30 (visit window: day 30 – 32), after randomisation. Participants/LAR will be asked to consent to being contacted by study staff for the follow-up visits to minimise loss to follow-up. In case of failure to successfully contact participant/LAR at the end of trial participation, the participant's general practitioner/family doctor will be contacted to complete information on the primary endpoints.
- **Extension study** – in a subset of patients (around 300 patients per arm), patients that were initially hospitalised will be followed post-discharge at month 3 (visit window: +7 days) and month 6 (visit window: +7 days) to study health economic and social impact.
- Qualitative Evaluation: Only clinician (semi-structured) qualitative interviews

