10.5. Baseline and follow-up data for health-economic analysis

Follow up Assessments: Timepoints: Day 1, Day 14 and Day 30. · 3 months and 6 months for patients included in Extended Follow up

Individual patient data will be clustered in four main categories:

patient status prior to consultation (including quality of life assessment), diagnostics (including microbiological diagnostic tests and thoracic imaging), medicines (antibiotics and any other prescribed medication at the ER/admission including several parameters, antibiotic prescription in the previous 14 days) and patient follow-up (quality of life, adherence to treatment, duration of complaints).

Quality of life- (see eCRF completion guidelines on guidance) The EQ-5D (<https://euroqol.org>) contains 5-dimensions ("5D") related to everyday living: mobility, self-care, usual activities, pain/discomfort, and anxiety/depression. Patients rate the problems they have with each of these dimensions on a 5-level scale ("5-L") from 1 (no problems) to 5 (extreme problems). The second part of the EQ-5D-5L asks patients to grade their current global health status from 0 (worst health you can imagine) to 100 (best health you can image). The questionnaire form takes ± 5-10 min to administer. It needs to be completed by patient or person who has known the patient for > 5 years. (Order of preference: caregiver > spouse > children 18+ > sibling > other acquaintance). For patient questionnaires, patients will receive a link per email to complete the questionnaires online, which will directly be incorporated into the eCRF and be regarded as source data once digitally completed by the patients. If this is not possible or if patients are seen face to face, questionnaires will be completed per paper (source data) and entered in the eCRF by study staff at the site. In this case paper versions will be stored as source data. The third option to have the questionnaires completed is the use of the Interviewer version in which the study staff will interview the patient and complete the data on the paper form (source data) after which data will be entered in the eCRF.

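### Recent antibiotic prescription is listed for collection but not named as a covariate in the antibiotic-days model; naming it would be a cheap, modest gain in precision.

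*Combined protocol and SAP*

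**What the plan says.** **Collection.** Section 10.5 of the protocol groups the individual patient data into four categories. The one on medicines includes "antibiotic prescription in the previous 14 days". Section 10.3 states: "Information including data for health economic analysis will be collected on day of enrolment".

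**Models.** Section 13.3 fits linear regressions for antibiotic days and for days alive out of hospital, "including as covariates stratification by age groups and predefined risk factors". The adverse outcome is analysed by "Cox proportional hazards regression adjusted for age groups and predefined risk factors".

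**Risk factors and strata.** Section 13.2 gives the risk factors by example, as groups likely to develop severe disease: the elderly and "patients with chronic pulmonary, cardiovascular or metabolic disease or immunocompromised patients". Its other analysis strata are age group, clinical syndrome and vaccination status. On allocation, section 10.2 says: "Randomisation will be stratified by centre".

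**Status of the SAP.** Section 13.2 also says: "A statistical analysis plan will be prepared after protocol approval". The text supplied contains no separate SAP, so the full list of risk factors cannot be read anywhere.

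**The concern.** Antibiotic days within 14 days is a co-primary superiority endpoint. Whether a patient had already been prescribed an antibiotic in the preceding fortnight is plausibly one of the closer baseline predictors of it. The eligibility rules leave room for such patients. Section 8.2 admits illness of up to 14 days, and section 8.3 has no exclusion for antibiotics already taken for the present illness.

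In a linear model, adjusting for a prognostic baseline variable narrows the confidence interval and leaves the treatment contrast unchanged in meaning. It also removes the part of a chance imbalance between arms that the variable explains. The plan intends to collect this variable but mentions it only as a health-economic item. What is at stake is some precision on one endpoint that could be had at almost no cost.

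**Working it through.** **1. Where the item is named**

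| Place in protocol | Prior antibiotic prescription named? |
|---|---|
| 10.5, data for health-economic analysis | Yes |
| 10.2, randomisation strata | No (centre only) |
| 13.2, analysis strata and risk factors | No |
| 13.3, co-primary model covariates | No |

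**2. The plan's own figures.** Inputs from section 13.1: difference 1 day, SD 4, power 0.90, non-normality factor 1.15, and "the two superiority endpoints will be tested using a two-sided alpha of 0.025".

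- Superiority: n per arm = 1.15 × 2 × SD² × (z for alpha + z for power)² / difference² = 1.15 × 2 × 16 × (2.2414 + 1.2816)² = 1.15 × 397.16 = 456.7, so 457. This matches the plan.
- Non-inferiority: 10% incidence in both arms, margin 5 points, one-sided alpha 0.05, power 0.95. n per arm = (1.6449 + 1.6449)² × 2 × 0.10 × 0.90 / 0.05² = 779.2, so 780. This also matches and is what sets the trial size.

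**3. Variance explained by a none / any covariate.** R² = q(1 − q)D²/SD², where q is the share with a prior prescription and D their mean difference in antibiotic days. Assumptions, since the documents give neither: q from 15% to 30%, D from 1 to 3 days. SD 4 is the section 13.1 figure for days alive out of hospital. Section 13.1 says only that the SD for antibiotic days should be smaller, so SD 3, the lowest row of the sample-size table, is shown as well.

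- SD 4, low: 0.15 × 0.85 × 1/16 = 0.8%
- SD 4, high: 0.30 × 0.70 × 9/16 = 11.8%
- SD 3: 0.1275/9 = 1.4% to 0.21 × 9/9 = 21%

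**4. Effect on the confidence interval.** Width ratio = √(1 − R²).

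- SD 4: √0.992 = 0.996 to √0.882 = 0.939, so about 0.4% to 6% narrower.
- SD 3: √0.986 = 0.993 to √0.79 = 0.889, so about 0.7% to 11% narrower.

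At 780 per arm and SD 4, the 97.5% half-width without the covariate is 2.2414 × 4 × √(2/780) = 0.454 day. With it, the half-width is 0.454 × 0.996 = 0.452 to 0.454 × 0.939 = 0.426 day.

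**5. Effect on power for 1 day at 780 per arm.** The sample size is divided by 1.15, as in the plan's correction.

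| SD | R² = 0 | R² = 0.05 | R² = 0.10 |
|---|---|---|---|
| 4 | 99.1% | 99.3% | 99.6% |
| 5 | 92.5% | 93.8% | 95.0% |

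At SD 3 power is about 100% throughout.

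**6. Size of a chance imbalance.** A 1.96-standard-error difference in q between arms is 1.96 × √(2q(1 − q)/780). That is 3.5 points at q = 15% and 4.5 points at q = 30%. Multiplied by D, the unadjusted contrast would shift by 0.035 × 1 = 0.04 to 0.045 × 3 = 0.14 day, against a target of 1 day.

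**The case against.** The strongest reply is that nothing important depends on this. Section 13.1 calls antibiotic days non-limiting, the trial is sized by non-inferiority, and power is already near its ceiling at the planning SD. That stands. Even at the top of the assumed range for SD 4, the half-width improves by only about 0.03 day.

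Several stronger readings are tempting, and the documents do not support them.

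- *The variable is excluded from the models.* The risk-factor description in section 13.2 is open-ended and the SAP is still to come. The supported statement is that the variable is not named. The open list does not show that it is covered either, since the description concerns risk of severe disease.
- *It is recorded for every patient before randomisation.* This is a reasonable inference from sections 10.3 and 10.5, but neither completeness nor timing relative to randomisation is stated.
- *All three co-primary analyses lose precision.* No gain has been worked out for days alive out of hospital or the adverse outcome, and the documents give nothing to base one on.
- *The analysis is biased or underpowered.* Randomisation and a valid interval already allow for chance imbalance.

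Two further points reduce the expected gain. Section 8.2 frames entry around waiting for the result before starting antibiotics or discharging the patient, and section 8.3 excludes patients within 14 days of their last respiratory infection. Both may lower the share already treated, although treatment for the current illness remains possible. The R² above also ignores overlap with age and chronic disease, which the model already contains.

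**Conclusion.** The point holds as a low-priority, nearly free improvement. The protocol plans to collect a plausible baseline predictor of a co-primary endpoint and does not name it in that endpoint's model.

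The benefit rests on the assumed share, difference and SD in the working, none of which the documents give for antibiotic days. A reader might infer from it that the trial needs more patients or that its main comparison is unsound. Neither follows: the gain is in efficiency only, and its upper end needs the most favourable of the assumptions.

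**What to change.** In section 13.3 and the SAP, before any outcome data are seen:

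1. Name antibiotic prescription in the 14 days before enrolment, coded none / any, as a fixed covariate in the linear model for antibiotic days.
2. Confirm that the item is recorded for every patient and that its reference period ends before randomisation, so that an antibiotic prescribed at the study ER visit is not counted.

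Three extensions are optional: adding the term to the other two co-primary models, separating completed from ongoing courses, and a prespecified interaction with allocation. Separating completed from ongoing courses may need more eCRF detail than section 10.5 lists.

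The cost is one model term, a sentence of SAP text and a check of the eCRF item. No patients are added.
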